6.2 Overall strategy of efficacy analyses

An overall overview of the strategies for efficacy analyses is listed in Table 5 . A detailed description of each endpoint will be described in following sections.

Table 5: Overall overview of strategies for efficacy analyses

	Hypothetical strategy	Treatment policy strategy	observed case
Primary endpoint	- Main estimator - Sensitivity estimator - Sensitivity estimator (tipping point)	- Main estimator - Sensitivity estimator	√
Key secondary 2-6 ¹	- Main estimator - Sensitivity estimator	- Main estimator - Sensitivity estimator	√
Secondary 7-9 ¹	- Main estimator - Sensitivity estimator		√
Secondary endpoints ²	- Main estimator		
Immunology parameters			√

¹ Key secondary and secondary endpoints in the testing hierarchy

² Binomial endpoints will be analysed under the hypothetical strategy using the same imputation rules as for the primary endpoints, however the estimator is different.

6.3 Primary endpoint analysis

6.3.1 Definition of endpoint

The primary endpoint is the average TCS during the BPS. The average TCS during the BPS is the average of the daily sum of the DSS and DMS during the BPS.

6.3.2 Main estimator, sensitivity estimator(s) and statistical analysis for the trial product and treatment policy estimands

The main estimator for both estimands will be the absolute treatment difference.

The main estimator for both estimands will be based on an identical method of statistical analysis (specified below), although the actual data used in each analysis may vary according to the different strategies taken for the handling of intercurrent events and missing data. Further details of the different strategies for each estimand are provided in sections 6.3.3.1, 6.3.3.2, and 6.4.1.

Analyses will be based on all randomised subjects. Subjects for whom the efficacy endpoint is missing will be included in the analysis through multiple imputation, where missing data will be

imputed from the same age group according to the approaches specified in sections 6.3.3.1, 6.3.3.2, and 6.4.1. Imputation will use the method of unrestricted random sampling with replacement (seed=7127) and 1000 multiply imputed datasets will be created. For each dataset, the efficacy endpoint will be square root transformed in order for the residuals to fulfil the underlying assumption of following the so-called statistical normal distribution and analysed using a linear mixed effects model assuming unequal variances in the 2 treatment groups. The model will include treatment, cohort (1, 2), and age group (5-11 years, 12-17 years) as fixed effects and pollen station within cohort as a random effect, with different residual errors specified for each treatment group. The model will be estimated using REML, and the denominator degrees of freedom will be calculated using the Kenward and Roger's approximation (Kenward and Roger 1997).

Rubin's rule is used to combine the 1000 analysis results across the multiple imputed datasets. The p-value for the absolute difference is reported as the test result.

The results are back-transformed as follows; after Rubin's rule is used to combine results across imputations, estimated least square means on the square root transformed scale are output along with the associated covariance matrix. The absolute difference is calculated by squaring the adjusted means, and then calculating the difference. For the absolute difference the SE is approximated by using the first order Delta method (first order Taylor approximation), and from this the 95% CI is calculated. For the relative difference, Fieller's theorem (Fieller 1954) is used to calculate the 95% CI. More details can be found in Appendix B.

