6.1 General considerations

Continuous data will be summarised by treatment group using mean, standard deviation, median, minimum, and maximum. Categorical data will be summarised by treatment using frequency tables displaying numbers and percentages. For the tabulations of data by visit an observed case approach is used.

All the statistical tests described in this document use a significance level of 5% and all tests and confidence intervals are two-sided. The null hypothesis is the hypothesis of no difference between treatment groups and the alternative to the null hypothesis is the hypothesis of difference. For each analysis the specific test is described in more detail.

The number of imputations will be increased from 1000 to 10000 if the actual significance level of the performed test is estimated to be between 4%-6%. This will be done to ensure the precision of estimated standard error, and thus the right hypothesis testing conclusion will be made.

Baseline values are defined as the latest available observation at or prior to the date of the first administration of IMP, unless otherwise defined.

Collected age at randomisation will be used to derive the medication score throughout the pollen season.

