6.3.3 Handling of intercurrent events and missing data

Subjects for whom the endpoint is missing because of missing diary data or missing pollen exposure (see Section 9.1), multiple imputation will be from own treatment group in case of no intercurrent event has occurred, otherwise below imputation rules will be applied. Data is assumed to be MAR.

Subjects with imputed endpoint, will be included in the statistical model with their original treatment group, age group, cohort, and pollen station.

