6.11 Changes and/or deviations to protocol-planned analyses

In addition to the analyses specified in the CTP a supplementary analysis for the primary endpoint has been added where subjects with potential data issues will be excluded from the main analysis.

The secondary endpoints (average TCS during the AHPS and OPS, average DSS during the AHPS and OPS, average DMS during the AHPS and OPS, and average TCS (EAACI scoring) during BPS and TPS) will be analysed by using the hypothetical estimand and main estimator only.

Local administration site reactions are specified as 'treatment-related local administration site TEAEs.

The reasons for IMP discontinuation will be visualised by a band plot, instead of a Kaplan-Meier plot as the band plot also shows the different reasons for discontinuation.

Physical examination will not be summarized by visit as stated in the CTP, instead a shift table will be made from baseline to end of treatment. 5-, 25-, 75-, and 95 percentiles will not be presented for tabulation of data by visit as stated in the CTP.

The exploratory assessment of the levels of serum antibodies/serum components/serum markers to relevant allergens will not be performed nor reported in a separate document as stated in CTP.

Due to the amount of missing pollen data, it was deemed necessary to perform a visual inspection of all species by pollen station instead of the pollen plots (pollen grains/m³ versus time) as the approach chosen is more precise.

7 Sample size determination

Sample size calculations are based on the primary endpoint, the average TCS during the BPS, which will be square root transformed prior to analysis in order to better approximate the normal distribution. Based on previous ALK SLIT-tablet studies in both adult and paediatric populations, it is assumed that the mean of the square root transformed average TCS during the BPS in the placebo group is 2.5 with corresponding common standard deviation of 1.4 in both placebo and active groups.

Analyses for the primary and secondary estimands will include all randomised subjects and use different multiple imputation strategies to account for missing data. For the purposes of sample size estimation, it is assumed that 5% of observations in the active arm are imputed from the placebo arm. A true relative treatment effect of 25% is assumed, which corresponds to an effective relative treatment effect of 23.75% after placebo imputation.

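### Imputation donors are matched on arm and age group but not on cohort, so the treatment effect is biased if missingness follows an arm-by-cohort interaction

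*SAP*

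**What the plan says.** SAP 6.3.2 sets the method for the primary endpoint: "Imputation will use the method of unrestricted random sampling with replacement (seed=7127) and 1000 multiply imputed datasets will be created". Missing values are "imputed from the same age group according to the approaches specified". SAP 6.3.3 to 6.3.3.2 then fix the donor arm:

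- Own arm: no intercurrent event, or discontinuation unrelated to treatment.
- Placebo: discontinuation for lack of efficacy.
- Treatment-related adverse events: own arm for the trial product estimand, placebo for the treatment policy estimand.

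The sensitivity estimators (6.3.3.4, 6.3.3.5) change the donor arm or add a penalty. Section 6.4.1 carries the approach to the key secondary endpoints, and 6.7 uses age group and treatment group for the proportion endpoints. Appendix B and protocol 15.12.1 add no further matching variable.

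The analysis model has treatment, cohort and age group as fixed effects and pollen station within cohort as a random effect. Under 6.3.3, imputed subjects "will be included in the statistical model with their original treatment group, age group, cohort, and pollen station". SAP 3.2 equates cohort 1 with the 2022 seasons and cohort 2 with the 2023 seasons.

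**The concern.** An imputed score carries the donor's season, but the model treats it as belonging to the recipient's season. The imputation therefore conditions on less than the analysis does. Own-arm imputation is labelled missing at random, but as specified this needs missingness to be unrelated to outcome given arm and age group alone.

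The protocol's own reasoning points the other way. Section 15.15 declines to impute daily diary values because they depend on local pollen exposure and on the individual subject. Endpoint imputation then disregards which season the subject was exposed to.

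If mean scores differ between cohorts, pooled donors pull the imputed values towards a mixture of the two seasons. If that pull differs between arms, it enters the treatment contrast of the primary analysis and of the key secondary analyses that follow it in the testing hierarchy. None of the planned sensitivity estimators changes the pooling.

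**Working it through.** **1. Planning figures (SAP section 7).** Inputs: "the mean of the square root transformed average TCS during the BPS in the placebo group is 2.5"; an SD of 1.4 on that scale in each arm; and "A true relative treatment effect of 25% is assumed, which corresponds to an effective relative treatment effect of 23.75% after placebo imputation". SAP 6.1 gives the level: "All the statistical tests described in this document use a significance level of 5% and all tests and confidence intervals are two-sided".

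- Full analysis set: effect = 2.5 − 2.5 × √(1 − 0.2375) = 0.317; SE = 1.4 × √(2/500) = 0.0885; power 94.7% (SAP Table 7: 95.0%).
- Observed case: effect = 2.5 − 2.5 × √0.75 = 0.335; SE = 1.4 × √(2/450) = 0.0933; power 94.8% (Table 7: 94.7%).

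Table 7 reproduces, so 0.335 is used as the planned effect on the root scale.

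**2. Bias from pooled donors.** Let g be the 2022 minus 2023 mean on the root scale, m1 and m2 the missing fractions in cohorts 1 and 2 of one arm, with equal cohorts and own-arm donors. The share of donors from cohort 1 is p = (1 − m1)/(2 − m1 − m2).

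- Arm mean after imputation, relative to the 2023 mean: (g/2) × [(1 − m1) + p(m1 + m2)].
- True value: g/2.
- Bias in that arm: (g/2) × (m2 − m1)/(2 − m1 − m2).

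The bias in the treatment effect is the placebo value minus the active value.

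| Missing 2022/2023, active | Missing 2022/2023, placebo | Bias ÷ g | g = 0.4 | g = 0.8 | Share of 0.335 |
|---|---|---|---|---|---|
| 15% / 5% | 5% / 15% | 0.0556 | 0.022 | 0.044 | 7% to 13% |
| 12% / 8% | 10% / 10% | 0.0111 | 0.004 | 0.009 | 1.3% to 2.7% |
| 15% / 15% | 5% / 5% | 0 | 0 | 0 | 0 |
| 15% / 5% | 15% / 5% | 0 | 0 | 0 | 0 |

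First row: active (g/2)(−0.10)/1.80 = −0.0278g; placebo +0.0278g; difference 0.0556g. With g positive this exaggerates the effect; the mirror-image pattern dilutes it.

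**3. Simulation check.** Assumptions: 1,000 subjects, equal cohorts, 33 stations per cohort, 10% missing overall, 1,200 trials per scenario, 60 imputations, station fitted as a fixed effect.

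- Crossed 15%/5% pattern, no true effect, gaps of 0.5 and 1.0: mean estimate 0.032 and 0.060 with the planned donors, 0.003 and 0.004 with cohort added. The reductions, 0.029 and 0.056, match the formula (0.028 and 0.056).
- Type I error in those scenarios: 6.7% and 9.7% with the planned donors, 5.4% in both with cohort added (Monte Carlo error about 0.6 points).
- Equal missingness in both arms: estimate 0.338 under both rules, power 96.9% under both, type I error 5.4% and 5.3%.

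**4. Did the seasons differ?** In Appendix D the unweighted mean of the stations' birch averages is 403 grains/m3 in 2022 (29 stations) and 253 in 2023 (35 stations). At the 26 stations with both values the 2022/2023 ratio has median 1.8 and range 0.17 to 8.2. Ten of the 26 were higher in 2023.

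**5. Donor-pool uncertainty.** With missing fraction f and many imputations, Rubin's variance is s²(1 + f)/n and the true variance is s²/[n(1 − f)]. The SE ratio is √(1 − f²). At f = 0.10 it is 0.995, so the SE is 0.5% too small and type I error is 5.12%.

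**6. Donor cells with cohort added.** Children: 1000 × 0.45 ÷ 4 × 0.9 = 101 donors per cell. Matching on station instead: about 65 station-cohorts × 2 arms × 2 age groups = 260 cells, or 1000/260 = 3.8 subjects per cell.

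**The case against.** The strongest reply is that the bias needs a particular pattern. In a double-blind trial randomised within country and age group, more dropout in one arm, or in one year, does no harm. Only their interaction does, and a mild one costs at most 0.009, about a tenth of the planning SE of 0.0885. That stands, and it sets the size of the point.

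The observed-case analysis adjusts for cohort and station without imputation, and the tipping-point analysis stresses the imputed values. Both help only in part. Under SAP section 5 the observed-case analysis includes diary data after discontinuation, so it is not a like-for-like check on the trial product estimand. The tipping point applies to the primary endpoint only and penalises only the active arm.

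A reader might infer more than the documents support:

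- **That the pollen counts establish a score gap of 0.4 to 0.8.** They do not. No document converts grains/m3 into a symptom or medication score. The averages are not weighted by subjects, and six cohort 2 birch values repeat a neighbouring station.
- **That the problem is worst where a whole station lacks a season**, since 6.3.3 covers endpoints missing because of "missing diary data or missing pollen exposure". When a station-cohort is missing, both arms go missing together, which is close to the harmless case. For birch, only PLKATO in cohort 2 appears to lack a season while having others.
- **That Rubin's variance is materially wrong because donors are not resampled.** The shortfall is 0.5% of the SE at 10% missing. Ignoring station can push the other way: with an assumed station SD of 0.9, Rubin's SE was 0.079 under the planned rule and 0.072 under a model with station.

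**Conclusion.** The concern holds as a conditional weakness in the primary and key secondary analyses. The donor rule leaves out cohort although the model includes it, so the missing-at-random assumption is narrower than it needs to be. The treatment effect is exposed to bias under an arm-by-cohort interaction in missingness.

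The size runs from zero, through about 1% to 3% of the planned effect for a mild interaction, to 7% to 13% for a strongly crossed one. These figures assume equal cohorts, gaps of 0.4 to 0.8 on the root scale and the stated missingness patterns, none of which the documents give. The documents do not show that the estimate will be biased. At the planned 10% missing, with arms alike within cohort, effect, power and type I error barely move. The case for changing the rule is that a known route to bias can be closed at little cost.

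**What to change.** In SAP 6.3.2 and Appendix B, draw donors within arm (or placebo, where the rule says so) × age group × cohort. Apply the same cell to the sensitivity estimators in 6.3.3.4 and 6.3.3.5, the key secondary endpoints in 6.4.1 and the proportion endpoints in 6.7. Record it in 6.11 as a change from protocol 15.12.1, before unblinding.

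The cost is one more matching variable, that documented deviation and smaller cells: about 100 child donors each if cohorts are equal, fewer in the smaller cohort if they are not. Matching on station is not proposed, because about four subjects per cell is unworkable. Cohort matching therefore leaves differences between stations within a season unaddressed.

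An optional refinement is to bootstrap the donor pool before each draw (approximate Bayesian bootstrap). The gain at 10% missing is too small to require it.

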3.2 Trial design

This is a phase III, randomised, parallel-group, double-blind, placebo-controlled, multi-regional trial in children (5-11 years) and adolescents (12-17 years) with AR/C, with or without asthma, induced by pollen from birch. Based on previous trials, it is anticipated that most subjects allergic to birch will also have AR/C induced by pollen from the birch homologous group.

Approximately 1000 subjects were to be randomised (1:1) and receive treatment with the SQ tree SLIT-tablet or placebo. The randomisation was stratified by geographical location (country) and by age group (5-11 years and 12-17 years).

[figure not shown]
The trial consisted of 3 periods: a screening period, a treatment period, which included pre-seasonal and co-seasonal treatment, and a follow-up period (Figure 1). The trial consisted of 2 cohorts; subjects in cohort 1 were randomised in 2021 and received treatment during the pollen seasons of 2022; subjects in cohort 2 were randomised in 2022 and received treatment during the pollen seasons of 2023.

Figure 1: Overall trial design

The screening visit took place up to approximately 6 months prior to randomisation. Once randomised, subjects were treated for at least 12 weeks prior to the start of the TPS. Treatment continued until 1 week after the end of the TPS, corresponding to up to approximately 12 months of treatment.

[REDACTED]
[REDACTED]
[REDACTED] Open-label rescue medication for allergic rhinoconjunctivitis was provided during the TPS [REDACTED]. Open-label asthma medication was provided to subjects with asthma during the TPS [REDACTED]. A follow-up phone visit was planned 1 week after the final treatment.

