8.4 Baseline characteristics

Demographic variables (age, age group, sex, race, ethnic origin, and country) will be summarised by treatment group.

Baseline characteristics (mono/poly sensitised, duration of AR/C induced by birch pollen, skin prick test results, skin prick test wheal sizes (birch), specific IgE to birch, and asthma status) will be summarised by treatment group.

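### The primary and key secondary models adjust for age group, cohort and pollen station but for no baseline measure of allergic disease; adding birch-specific IgE and asthma status is an optional precision gain of unknown size.

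*SAP*

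**What the plan says.** SAP 6.3.2 gives the primary model for the square root of the average TCS in the birch season: "The model will include treatment, cohort (1, 2), and age group (5-11 years, 12-17 years) as fixed effects". Pollen station within cohort is random and the residual variance differs by arm. The SAS code in Table 11 (Appendix C) matches. SAP 6.4.1 applies the same model to the key secondary endpoints.

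Two baseline measures of allergic disease are on file before the first dose. Protocol 4.1 (criterion I6) and 11.15 require birch-specific IgE at visit 1. Protocol 11.6 requires asthma history in the eCRF. SAP 8.4 only tabulates them: "skin prick test wheal sizes (birch), specific IgE to birch, and asthma status) will be summarised by treatment group". Baseline IgE serves as a covariate in one place, the immunology model for IgE itself (SAP 6.7.2).

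No pre-treatment TCS exists, because the eDiary is handed out at visit 4 and treatment starts at visit 2. Randomisation was stratified by country and age group only (SAP 3.2.3).

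**The concern.** Protocol 15.15 describes diary scores as driven by local pollen exposure and by the individual child's tolerance and medication use. Pollen station addresses exposure. Apart from age group, nothing in the model addresses differences between children. The planning SD is large (1.4 on a placebo mean of 2.5), and with no baseline TCS, disease covariates are the remaining route to reducing it.

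The criterion with least power would benefit most. In SAP Table 7, the chance that the lower 95% limit of the relative effect exceeds 10% is 60.2%, against 88.3% to 95.0% for the other three criteria.

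**Working it through.** **Inputs (SAP sections 3.2, 6.1 and 7).**
- Placebo: "the mean of the square root transformed average TCS during the BPS in the placebo group is 2.5".
- Spread: "corresponding common standard deviation of 1.4 in both placebo and active groups".
- Effect: "A true relative treatment effect of 25% is assumed, which corresponds to an effective relative treatment effect of 23.75% after placebo imputation".
- Imputation: "it is assumed that 5% of observations in the active arm are imputed from the placebo arm".
- Test: 5%, two-sided. Size: 500 per arm, 1:1.
- The planning simulation used a model with treatment only.

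**Step 1: reproduce Table 7 (FAS row).** On the square-root scale the active mean is 2.5 × √(1 − 0.2375) = 2.183, so the difference is 0.317.
- Significance: SE = 1.4 × √(2/500) = 0.0885. Power = Φ(0.317/0.0885 − 1.960) = 94.7%.
- Absolute effect above 1: effect = 2.5² − 2.183² = 1.484. Delta-method SE = 2 × √[(2.5² + 2.183²) × 1.4²/500] = 0.416. Φ(0.484/0.416) = 87.8%.
- Relative effect above 15%: with r = √0.85, Φ{(2.5r − 2.183)/√[(1 + r²) × 1.4²/500]} = 92.4%.
- Lower limit above 10% (Fieller condition): with r = √0.90, Φ{(2.5r − 2.183)/√[(1 + r²) × 1.4²/500] − 1.960} = Φ(0.1887/0.0863 − 1.960) = 59.0%.

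The plan states 95.0 / 88.3 / 92.8 / 60.2%. A simulation of 20,000 trials, with 5% of the active arm drawn from placebo, gives 95.0 / 88.2 / 92.7 / 59.4%. The observed-case row (450 per arm, 25% effect) gives 94.8 / 90.1 / 94.0 / 62.2% against a stated 94.7 / 89.9 / 93.9 / 62.2%. The planning figures reproduce.

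**Step 2: add the covariates.** Let R² be the share of residual variance that IgE and asthma explain, given the terms already in the model. The documents give no value, so 0-10% is an assumption. The SD becomes 1.4 × √(1 − R²), and the equivalent number of extra subjects is 1000/(1 − R²) − 1000.

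| R² | SE reduction | Equivalent extra subjects | Significance | Absolute effect > 1 | Lower limit > 10% |
|---|---|---|---|---|---|
| 0% | 0% | 0 | 94.7% | 87.8% | 59.0% |
| 1% | 0.5% | 10 | 94.9% | 87.9% | 59.4% |
| 5% | 2.5% | 53 | 95.7% | 88.4% | 61.1% |
| 10% | 5.1% | 111 | 96.5% | 89.0% | 63.5% |

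**Step 3: dilution by imputation.** Missing endpoints are drawn at random from the same age group and the assigned arm (SAP 6.3.2 and 6.3.3), so imputed values are unrelated to the child's own IgE or asthma status. If 10% are imputed (assumption), the slopes shrink to about 0.9 and the explained share to 0.81 × R². At R² = 10% the SE reduction falls from 5.1% to 4.1%, and the last column from 63.5% to 62.6%.

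**Step 4: effect on the back-transform.** SAP 6.3.2 and Appendix B square the adjusted means, so both effect measures depend on where those means are evaluated. Table 11 sets no weighting option, and a class-coded asthma term would by default be weighted 50:50. Illustration (assumptions: 30% have asthma, asthma raises scores, asthma R² = 2%, constant treatment effect on the square-root scale):
- Gap between asthma groups = √0.02 × 1.4/√(0.3 × 0.7) = 0.432.
- Both means shift by (0.5 − 0.3) × 0.432 = 0.086, to 2.586 (placebo) and 2.269 (active).
- Absolute difference: 1.48 becomes 1.54. Relative effect: 23.75% becomes 23.0%.
- Chance of a lower limit above 10%: 57.8%. With observed-margin weighting at the same R² it would be 59.8%.

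Adding asthma carelessly could therefore worsen the criterion it is meant to help.

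**The case against.** The strongest defence is that the model already uses the baseline information that the protocol gives reasons for. Age group is a baseline variable and a randomisation stratum. Pollen station carries local exposure, which is the protocol's reason for stratifying by location (3.2). The covariate set follows the structure in Protocol 15.12.1. No section calls IgE or asthma prognostic for TCS or reports a correlation. Eligibility also narrows the range: IgE of at least 0.70 kU/L and moderate to severe disease. The sample size targets at least 85% power for requirements 1 to 3, and the stated 95.0, 88.3 and 92.8% come from a treatment-only model. The criterion at 60% lies outside that target. At R² = 1% it gains 0.4 points, against a Monte Carlo error of about 1.5 points in the plan's own 1000-trial simulation.

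All of this stands, and it rules out three stronger readings that a reader might infer:
- That the model ignores baseline prognosis altogether. It does not, as age group and pollen station show.
- That precision is certainly being lost, or that the trial is underpowered for its target. The documents support neither.
- That chance imbalance in IgE or asthma would bias the result. Omitting a covariate neither biases a randomised comparison nor inflates type I error. The standard error already reflects chance imbalance, and SAP 8.4 would make it visible.

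The defence does not remove the narrower point. Two disease measures that are already collected are left out of the model, and including them costs very little.

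**Conclusion.** The point holds as an optional efficiency improvement, not as an error in the plan. No baseline measure of allergic disease is in the primary or key secondary models, although two are available for all randomised children. Under an assumed R² of 0-10%, the standard error falls by 0-5.1% and power for significance rises by at most about 2 points (94.7% to 96.5%). The chance of a lower limit above 10% rises from about 59% to at most about 64%, before dilution from imputation. The true R² could be near zero, and the gain would then be negligible.

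**What to change.** Before unblinding, amend SAP 6.3.2, 6.4.1, Table 10 and Table 11:
- Add log10 screening birch-specific IgE (continuous) and asthma status (yes/no) as fixed effects for the primary and key secondary endpoints.
- Evaluate the adjusted means at the observed covariate distribution, for example with the OM option and FAS margins, or with asthma as a mean-centred numeric term. The OM option would also reweight cohort and age group; mean-centred coding affects only the new term.
- Keep the present model as a pre-specified supportive analysis.

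A smaller change would be to leave the primary model alone and pre-specify the adjusted model as supportive. If unblinding has already taken place, the adjusted analysis can only be reported as post hoc.

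Cost: SAP wording, two model terms, two of roughly 1000 degrees of freedom and one extra table. No new data are needed. The downside to state is that the gain may be small or nil if the covariates prove weakly prognostic.
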